OXYASP STUDY PROTOCOL

HRA APPROVAL NUMBER: ID: 15/LO/1086

FINAL VERSION COMPLETED MAY 2017

Study Design and Procedures

In a double-blind, placebo controlled, randomised crossover design, participants self-administered, under instruction from the researcher, 40 IU of IN-OT (Syntocinon; Novartis, Basel, Switzerland) or placebo (identical composition to Syntocinon except for the omission of oxytocin). Participants began the morphed faces task within 25-30 minutes of administration. The oxytocin dose employed was the highest clinically applicable safe dose administered to human volunteers, in keeping with a protocol which demonstrated significant neural activation over a period of 25–78 minutes with this dose (Paloyelis, Doyle et al. 2016). At a second session (occurring between three and twenty-eight days later), participants completed the fMRI task again under the alternative treatment condition. Participants were instructed to avoid food, drinks (except water), and nicotine two hours before starting the experiment. Participants completed the Morphed Faces task (see Figure 1). During the task, participants were asked to indicate the sex of each face with a left-right button press using the index and middle finger of their right hand during a single run, which lasted 9 minutes 56 seconds.

General linear model analysis of behavioural data

For the Morphed Faces task, means were first calculated across the whole sample for both accuracy and reaction time in rating the gender of the faces displayed. To investigate the effect of oxytocin and its interaction with other variables, for both accuracy and response latency data, a three group (NO, ASPD-P, ASPD+P) by two condition (oxytocin, placebo) by four intensity (40%, 60%, 80%, 100% of fearful facial expression) repeated-measures analysis of variance was conducted. Post-hoc

repeated-measures analysis of variance was performed for ASPD-P vs ASPD+P. SPSS version 25.0 was used. A threshold for significance of p <0.05 (corrected) was set for all tests.

Primary outcome measure and MRI processing

Whole-brain blood oxygen level dependent (BOLD) fMRI data were acquired using a 3.0 Tesla General Electric Magnetic Resonance Scanner. The principle outcome measure was a regressor for modulation of neural activity (BOLD responsivity) by intensity of fearful expression. Specific MRI parameters, and full details of preprocessing and individual level analyses are available in supplementary materials.

MRI Data group analysis

Following preprocessing steps, modulated emotion data were entered into a 3 Group (NO, ASPD-P, ASPD+P) by 2 Condition (placebo, oxytocin) 3dMVM (ANOVA style computations) model. Within this framework, general linear tests were coded to assess differential effects of drug between the groups. Post hoc t-tests were conducted to decompose these interactions by examining between-and within- group effects. Correction for multiple comparisons was performed using a spatial clustering operation in AFNI's 3dClustSim, using the autocorrelation function (-acf) with 10,000 Monte Carlo simulations for the whole-brain analysis. Spatial autocorrelation was estimated from residuals from the individual-level GLMs. The initial threshold was set at p = 0.005. As outlined above, bilateral amygdala, anterior insula and midcingulate cortex, were selected a priori for ROI analysis. Small-volume corrections, calculated using an anatomically defined mask (TTN27, a Talaraich atlas from AFNI), yielded thresholds of k = 13 for anterior/mid-cingulate cortex, k = 8 for anterior insula, and k = 2 for amygdala at an initial significance threshold of 0.005 (multiple comparison corrected p<0.05).

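### Must the behavioural analysis spell out what its corrected 5% threshold means?

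*Combined protocol and SAP*

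**What the plan says.** The combined protocol and SAP, under *General linear model analysis of behavioural data*, sets the aim as "To investigate the effect of oxytocin and its interaction with other variables, for both accuracy and response latency data". The model is "a three group (NO, ASPD-P, ASPD+P) by two condition (oxytocin, placebo) by four intensity", with intensity at 40, 60, 80 and 100% fear. A post-hoc "repeated-measures analysis of variance was performed for ASPD-P vs ASPD+P" follows, and "SPSS version 25.0 was used". The only statement on error control in that section is "A threshold for significance of p <0.05 (corrected) was set for all tests".

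Under *MRI Data group analysis* the method is explicit: "Correction for multiple comparisons was performed using a spatial clustering operation", with small-volume thresholds for the regions chosen in advance. That section describes the resulting 5% level as corrected for multiple comparisons. Under *Primary outcome measure and MRI processing*, the principal outcome is the regressor for modulation of BOLD response by fear intensity. The supplement is cited there for MRI parameters, preprocessing and individual-level analyses only.

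**The concern.** The word *corrected* has no method attached to it in the behavioural section. The one method the document describes is spatial and cannot be applied to F-tests on accuracy or latency. Two kinds of correction would be natural here.

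- **Sphericity.** Intensity is a within-subject factor with four levels, so terms that contain it may need an epsilon adjustment.
- **Multiplicity.** Several oxytocin terms are tested on two outcomes, and no key term is named.

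The two can disagree on the same data. An oxytocin term without intensity and with p = 0.02 is significant if *corrected* means sphericity only, because no epsilon applies to it. It is not significant under Bonferroni over 8 tests, where the level is 0.05/8 = 0.00625. If the choice were made after seeing the data, a behavioural oxytocin claim could not be checked against the plan.

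**Working it through.** The plan gives no sample size, covariance or per-test level for the behavioural data, so there is no figure to reproduce. The check is a count of tests followed by a sizing of each reading. Total N and epsilon are assumptions throughout.

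**1. Count of tests.** Three factors give 2^3 - 1 = 7 terms per ANOVA. Four contain oxytocin condition: condition, group x condition, condition x intensity, and the three-way term. Two of those four contain intensity. Two outcomes give 4 x 2 = 8 oxytocin tests. Running the two-group ANOVA on both outcomes as well gives 16.

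**2. Sphericity only, each test at 0.05.** Under independence, the chance of at least one false oxytocin effect is 1 - 0.95^m:

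- m = 4: 18.6%
- m = 8: 33.7%
- m = 16: 56.0%

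**3. Bonferroni over 8.** The per-test level is 0.00625, and 1 - (1 - 0.00625)^8 = 4.9%.

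**4. Allowing for dependence.** The tests share error terms and participants, so familywise rates were simulated. All nulls were true, with three equal groups, N = 30, 60 and 120, epsilon 1.00, 0.86 and 0.77, correlation between outcomes 0 and 0.5, and 10,000 replicates per cell.

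| Meaning of *corrected* | 8 tests | 16 tests |
|---|---|---|
| Sphericity only | 30-33% | 40-45% |
| Bonferroni only | 4.5-7.9% | 3.8-7.3% |
| Both | 4.1-5.5% | 3.3-4.8% |

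The 16-test column assumes that the two-group ANOVA is run on both outcomes whatever the three-group result. If it is run only after a significant oxytocin term in the three-group ANOVA, it cannot raise the chance of at least one false effect when all nulls are true. The first-row figure then stays at 30-33%.

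**5. Size of the sphericity effect.** By Box's approximation, an unadjusted test has true level P(F(e·df1, e·df2) > F_0.95(df1, df2)), where e is epsilon. With N = 60 in three groups, df2 = 3 x (60 - 3) = 171.

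| Epsilon | Condition x intensity (df1 = 3) | Three-way (df1 = 6) |
|---|---|---|
| 1 | 5.0% | 5.0% |
| 0.75 | 6.7% | 7.0% |
| 0.5 | 9.1% | 10.0% |
| 1/3 (lower bound) | 10.9% | 12.6% |

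The effect is therefore modest or marked depending on an epsilon that the document does not give. Condition and group x condition are exempt, because condition has only two levels.

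**6. Which reading the text favours.** The threshold is said to cover all tests, yet an epsilon adjustment has no meaning for group, condition or group x condition. The imaging section uses the language of multiple comparisons, and the document never mentions sphericity. Both points lean towards multiplicity, so the 30-33% belongs to the less well supported reading.

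**7. Price of a fixed family.** A 1-df test with 80% power at 0.05 keeps Phi(2.802 - 2.734) = 53% at 0.05/8, and Phi(2.802 - 2.241) = 71% at 0.05/2. These are large-sample figures. The choice of family is a real trade-off with no single right answer.

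**The case for a change.** The strongest case for a change is that the plan promises a corrected threshold and a reader cannot tell what was promised. No redaction or missing figure accounts for this, and the supplement is not cited for it. The readings differ by a factor of about four or more (30-33% against 4.5-7.9%), and that gap barely moves with the assumed N or the correlation between outcomes. One or two sentences would close it, at no cost in data.

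Most of this stands as description. Method and family are unnamed, and the text does not say whether epsilon-adjusted p-values are used for intensity terms. It falls short of a needed change because the request is only to write down a choice the plan already commits to making. Labelling the behavioural tests exploratory, with no familywise claim, would satisfy it equally well. A request met by such different answers does not identify an analysis that is wrong.

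**Conclusion.** No change to the plan is needed. The behavioural section leaves out a detail that a trained analyst fills sensibly: a multiplicity adjustment over the oxytocin tests, with epsilon-adjusted p-values for the terms that contain intensity. SPSS offers those p-values. With both in place, the chance of at least one false oxytocin effect over the 8 tests is 4.1-5.5%. With Bonferroni alone it is 4.5-7.9%, and it would be higher if epsilon fell below the 0.77 simulated. The 30-33% arises only if *corrected* is taken to mean sphericity alone, which fits the wording less well.

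These figures rest on assumed N of 30 to 120, equal groups, assumed covariances and all nulls true. Even at their worst they concern accuracy and latency in a sex-judgement task. The principal BOLD outcome and its stated cluster correction are unaffected. What remains is a matter of documentation: the plan alone will not show which adjustment was intended.

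### The crossover models contain no session or treatment-order term, so any first-to-second-session change stays in the error of the drug tests; adding the term is a cheap gain in precision

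*Combined protocol and SAP*

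**What the plan says.** Under Study Design and Procedures the trial is a double-blind, placebo-controlled, randomised crossover with two sessions: "At a second session (occurring between three and twenty-eight days later), participants completed the fMRI task again under the alternative treatment condition".

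The primary outcome, under Primary outcome measure and MRI processing, is a slope: "The principle outcome measure was a regressor for modulation of neural activity (BOLD responsivity) by intensity of fearful expression". Under MRI Data group analysis, "modulated emotion data were entered into a 3 Group (NO, ASPD-P, ASPD+P) by 2 Condition (placebo, oxytocin) 3dMVM", and within that model "general linear tests were coded to assess differential effects of drug between the groups". Post hoc t tests between and within groups follow. The initial voxel threshold is 0.005, with cluster-based correction.

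Under General linear model analysis of behavioural data, accuracy and reaction time go into "a three group (NO, ASPD-P, ASPD+P) by two condition (oxytocin, placebo) by four intensity" repeated-measures ANOVA. After that, a post hoc "repeated-measures analysis of variance was performed for ASPD-P vs ASPD+P". On the significance level: "A threshold for significance of p <0.05 (corrected) was set for all tests".

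No section names session, period, order or sequence as a model term. The supplement is cited for scanner parameters and because "full details of preprocessing and individual level analyses are available in supplementary materials". The group-level models are written out in the main text and are not deferred to it.

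**The concern.** When a task is repeated, performance and brain response may change between the first and second occasion through practice, habituation or familiarity with the scanner. In a two-period crossover this change is tied to treatment order. It adds to the drug difference for those given oxytocin second and subtracts from it for those given oxytocin first. A model with Condition but no session or order term treats this predictable pattern as noise.

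The outcomes are not equally exposed. The imaging outcome is a slope on fear intensity, so a session change equal at all intensities cancels and only a session-by-intensity change matters. For mean accuracy and reaction time, a plain practice effect counts in full.

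At stake is mainly the power of the drug and drug-by-group tests. If order happened to be unevenly split, the estimates would also shift. The documents show neither a session effect nor an uneven split.

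**Working it through.** **Inputs from the documents.** Two sessions; three groups; Group x Condition (x Intensity) models; thresholds of 0.005 (voxel level) and 0.05 (behavioural). There is no stated power or sample-size figure to reproduce.

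**Assumptions, not from the documents.** 20 participants per group (60 in all); two-sided tests; pi from 0.1 to 0.8, in SDs of the within-person drug difference; order either balanced 10:10 in each group or set by simple randomisation.

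**Model.** For each participant, D = oxytocin minus placebo = tau_g + s x pi + e. Here s = +1 if oxytocin came second and -1 if first, pi is the session-2 minus session-1 change, and SD(e) = 1. With two within-person levels, a one-way model on D gives the same drug and drug-by-group tests as Group x Condition.

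**Effect of omission, balanced order.** The group means of D are unaffected because s averages to zero. The expected pooled error variance becomes 1 + pi^2 x 60/57, on 57 df. At pi = 0.5 this is 1 + 0.25 x 1.053 = 1.263, with square root 1.124. The 5% critical value of 2.002 then acts like 2.002 x 1.124 = 2.25, which on 57 df corresponds to a true level of about 0.028. The same steps give about 0.041 at pi = 0.3 and 0.012 at pi = 0.8. Simulation agrees.

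**Power of a between-group contrast of the drug effect.** The standard error is sqrt(2/20) = 0.316. Effects are set for 80% power at pi = 0: 1.195 SD at 0.005 and 0.901 SD at 0.05. Unadjusted power is simulated; adjusted power uses the noncentral t on 56 df.

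| Threshold | pi | Unadjusted, balanced | Unadjusted, random | Gain, balanced (points) | Gain, random (points) |
|---|---|---|---|---|---|
| 0.005 | 0.1 | 79.7% | 79.4% | 0.2 | -0.4 |
| 0.005 | 0.3 | 76.1% | 75.4% | 3.8 | 3.6 |
| 0.005 | 0.5 | 68.8% | 67.6% | 11.1 | 11.4 |
| 0.005 | 0.8 | 50.5% | 51.4% | 29.4 | 27.6 |
| 0.05 | 0.3 | 77.3% | 76.6% | 2.7 | 2.7 |
| 0.05 | 0.5 | 72.4% | 70.7% | 7.6 | 8.6 |
| 0.05 | 0.8 | 60.5% | 58.8% | 19.5 | 20.5 |

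With order in the model, power does not depend on pi: 79.9% (balanced) or 79.0% (random) at 0.005, and 80.0% or 79.3% at 0.05. Under random order the break-even lies between pi = 0.12 and 0.15.

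The drug main effect and the within-group paired test lose similar amounts. At 0.005 with balanced order and pi = 0.3, 0.5 and 0.8, unadjusted power is 76.2%, 68.7% and 50.6% for the main effect, and 76.0%, 68.3% and 50.8% for the paired test. With 15 or 25 per group the between-group figures hardly change (68.8% and 68.9% at pi = 0.5).

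**Uneven order.** Let p be the share given oxytocin second. The bias is pi(2p - 1) for the main effect, pi(2p_g - 1) within a group, and 2pi(p1 - p2) between two groups. At pi = 0.5:

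- 12:8 against 8:12 between groups: 2 x 0.5 x (0.6 - 0.4) = 0.20 SD; type I error at 0.05 is 0.061. A gap this large or larger has probability 0.268 under simple randomisation.
- 36:24 overall: 0.5 x (1.2 - 1) = 0.10 SD; type I error 0.078; probability 0.155 of a split at least this uneven.
- 14:6 within one group: 0.5 x (1.4 - 1) = 0.20 SD; type I error 0.097; probability 0.115 per group.

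These rates are conditional on the split. Averaged over simple randomisation, type I error is 0.050 to 0.051 for all three tests.

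**The case against.** The strongest reply is about weight. No session effect is shown, the tests keep their level on average, and the primary outcome is the least exposed because a uniform session change cancels from an intensity slope. The largest gains need pi near 0.8, for which the documents give no basis. Under random order with a very small session effect, adjustment loses a little power. All of this stands, and it is why the point is graded as a precision improvement only.

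The behavioural plan names an omnibus three-group ANOVA and a separate two-group ANOVA, whereas the 0.05 rows above are for a pairwise contrast with three-group error. That is fair, but the named tests behave alike. At the same effect, unadjusted and balanced, power at pi = 0, 0.3, 0.5 and 0.8 is about 82.5%, 79.3%, 73.4% and 57.7% (omnibus), and 79.4%, 76.7%, 71.7% and 59.6% (two-group).

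The text describes analyses in the past tense and does not say how order was randomised. If results are already known, changing the main model is a post hoc step and should be labelled as one. That affects how the change is reported, not whether the adjusted model is the better one.

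**Conclusion.** The point holds. Both group-level models omit session and order, and nothing in the documents suggests that the term appears elsewhere. This is a cheap improvement in precision, not a demonstrated failure of validity.

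Under the stated assumptions the loss in the drug-by-group contrast at 0.005 is negligible at pi = 0.1, about 4 points at 0.3, about 11 at 0.5 and 28 to 29 at 0.8. Where this trial falls in that range cannot be known from the documents, and the gain may be nil. The power figures are for a single test. Imaging inference is by cluster, so the 0.005 results do not translate directly to cluster-level power. The model assumes a session effect common to the three groups and does not address carry-over.

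**What to change.** Add treatment order (oxytocin-first or placebo-first, sum-to-zero coded) as a between-subject factor additive to Group, together with Order x Condition, which is the period effect. Do this in the 3dMVM model, in the behavioural ANOVAs (with Order x Condition x Intensity as well) and in the ASPD-P versus ASPD+P post hoc. A mixed model with session as a fixed effect is an alternative. Base the drug and drug-by-group tests on the adjusted model, and report order counts by group so that readers can judge any imbalance. If results are already known, show the unadjusted results alongside.

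Preferably take the within-group post hoc tests as general linear tests from the adjusted model. This is secondary to the core change and assumes similar variances across groups.

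**Cost.** No new data: randomised order is already held. One subject-level error degree of freedom per stratum is spent (57 to 56 with 60 participants; 38 to 37 in the two-group post hoc). With no session effect, power at 0.005 goes from 80.0% to 79.9% (balanced) or 79.0% (random); the two-group post hoc at 0.05 goes to 79.9% or 78.9%. Adjusting each within-group paired test separately costs more, from 80.0% to 79.3% or 76.5%. In the pooled model power goes from 87.0% to 87.0% or 86.2%; its higher starting point comes from pooling the error, not from the order term. Crossing Order with Group would allow different session effects by group, but it uses three degrees of freedom and gives 76.8% under random order, so it should not be the default.

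### The principal fMRI outcome is tested by an unranked whole-brain search and regional searches on the same maps, so it has no single decision rule controlled at 5%

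*Combined protocol and SAP*

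**What the plan says.** The section 'Primary outcome measure and MRI processing' defines the principal outcome as follows: "The principle outcome measure was a regressor for modulation of neural activity (BOLD responsivity) by intensity of fearful expression". It names no brain region, no contrast and no rule for calling the outcome positive.

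The section 'MRI Data group analysis' fits one group-by-condition model, within which "general linear tests were coded to assess differential effects of drug between the groups". The number of these tests is not given. Two searches of the resulting maps follow.

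- **Whole brain.** Cluster correction is done in 3dClustSim, "using the autocorrelation function (-acf) with 10,000 Monte Carlo simulations for the whole-brain analysis". No corrected level and no cluster extent are printed for this search.
- **A priori regions.** The text says that "bilateral amygdala, anterior insula and midcingulate cortex, were selected a priori for ROI analysis". Small-volume corrections "yielded thresholds of k = 13 for anterior/mid-cingulate cortex, k = 8 for anterior insula, and k = 2 for amygdala". All three extents are labelled as corrected to p<0.05.

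The cluster-forming threshold is stated once in general, "The initial threshold was set at p = 0.005", and repeated for the regions. The only statement from which a corrected whole-brain level can be taken closes the behavioural section: "A threshold for significance of p <0.05 (corrected) was set for all tests".

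Nothing in the supplied text says which search decides the principal outcome, makes one conditional on the other, divides alpha between them or calls either exploratory.

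**The concern.** Because the outcome has no location, a cluster in the amygdala and a cluster anywhere else in the brain can each be presented as a corrected result on the principal outcome. The two searches can disagree. All three a priori regions might be null while a cluster elsewhere passes the whole-brain threshold, or a handful of voxels might pass a regional threshold while the whole-brain search shows nothing. The plan does not say what the trial concludes in either case.

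If either result is enough, the chance of a false claim that oxytocin acts differently between groups is higher than the 5% attached to each search. This is separate from multiplicity across group contrasts. It is present with one contrast, and it remains if the three regions are treated as one perfectly controlled family.

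**Working it through.** **Inputs**

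- Corrected level for the regions: 0.05 (printed in 'MRI Data group analysis').
- Corrected level for the whole brain: 0.05 (inferred from the all-tests sentence in the behavioural section).
- Cluster-forming threshold: p = 0.005 (printed).
- Regional extents: k = 13, 8 and 2 (printed, one per region).
- Mask volumes, voxel size, smoothness parameters and sample size: not in the documents.

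**The plan's own figure.** The corrected p<0.05 is a declared level. The k values cannot be rebuilt without the missing inputs, so I take the level as stated.

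**Step 1: two routes, with the regions held jointly at 5%**

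- Independent searches: 1 − (1 − 0.05)(1 − 0.05) = 1 − 0.9025 = 0.0975.
- Upper limit, no overlap between false positives: 0.05 + 0.05 = 0.10.
- Lower limit, complete overlap: 0.05.

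**Step 2: allowing for nesting.** The regions lie inside the whole-brain mask, so the searches are not independent. The overlap was estimated by simulating smooth null Gaussian maps, 4,000 per setting. The cluster-forming threshold was two-sided p = 0.005, and each search was calibrated to exactly 5%. The brain mask (48,120 voxels), the regional masks and the two smoothness settings (Gaussian kernel SD 0.85 and 1.2 voxels) are assumptions.

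| Regions as share of brain mask | Kernel SD (voxels) | Whole brain or regional family | Whole brain or any of three separate regions |
|---|---|---|---|
| about 3% | 0.85 | 9.6% | 18.5% |
| about 3% | 1.2 | 9.4% | 18.2% |
| about 12% | 0.85 | 9.2% | 18.0% |
| about 12% | 1.2 | 9.2% | 18.0% |

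Overlap removes little. Most whole-brain false positives fall outside the regions, and a cluster just large enough for a region is usually too small for the whole-brain extent.

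Cluster extents are whole numbers, so real thresholds often sit a little below 5%. With integer extents and the smaller masks (3,000 maps per setting), whole brain or regional family gave 7.8% and 8.8%. Whole brain or any separate region gave 14.5% and 17.0%.

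**Step 3: three separate regional tests.** The separate k values suggest one 5% test per region.

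- Regions alone, independent: 1 − 0.95³ = 0.143 (14.3–14.5% simulated).
- Whole brain plus three regions, independent: 1 − 0.95⁴ = 0.185 (18.0–18.5% simulated).
- Upper limit for four searches: 4 × 0.05 = 0.20.

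**Step 4: after correction**

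- Regions decide, at 0.05/3 each: at most 3 × 0.05/3 = 0.05, and 1 − (1 − 0.05/3)³ = 0.049 if independent.
- Alpha split 0.025 and 0.025 between the regional family and the whole brain: at most 0.05, and 1 − 0.975² = 0.0494 if independent.
- Regions decide but keep separate 5% thresholds: still 0.143 if independent. Ranking without recomputing is therefore not enough.

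**The case against.** The strongest reply is that the plan never promises 5% across both searches. Cluster inference is region-specific: a claim about the amygdala and a claim about some other area are different hypotheses, each with its own correction. On that view the union rate matters only if any cluster counts as success for the trial, and the plan states no such rule. This stands as a limit on the finding. A reader might infer that the plan claims 5% and miscalculates it; the documents do not support that. The gap is that a named principal outcome has no rule for deciding it.

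A reader might also infer that the whole-brain search invalidates the small-volume corrections. It does not: each one controls error within its own mask, whatever else is run.

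Three further points stand in part.

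- The whole-brain 5% is an inference from a sentence in the behavioural section. It is plausible, since no other level is given, but it is not printed for that search.
- The regions are introduced with a reference to an earlier outline that is not in the supplied text. A ranking could have been stated there, so the absence can be asserted only for the text at hand.
- Choosing the regions a priori does set them apart from the wider search. It says when they were chosen, though, not that they alone decide the outcome.

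Running both searches may be customary, but custom does not supply a decision rule.

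**Conclusion.** The concern holds in a conditional form. The supplied text lets the principal outcome be called positive by either of two unranked searches. If the whole-brain search also runs at corrected 5% and either route counts, the false-positive rate per contrast is about 9–10% with the regional family held at 5%. That result assumes each search sits at exactly 5%; whole-number extents can bring it down to roughly 8–9%. If the three regional thresholds are separate 5% tests, the rate is up to about 18%.

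The 9.75% figure needs no assumption about volumes or smoothness, only independence. The simulated figures depend on assumed masks and smoothness but vary little across them. All figures are per contrast; several between-group contrasts would raise the rate further. This is a missing decision rule that is cheap to supply, not an arithmetic error and not a fault in the regional corrections themselves.

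**What to change.** In 'MRI Data group analysis', state that the decision on the principal outcome rests on the a priori regions (amygdala, anterior insula, midcingulate) as one family. Recompute the 3dClustSim thresholds so that the family-wise rate across all regions is 5%, using either a combined mask or alpha/3 per region. Report whole-brain clusters outside these regions as exploratory.

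Alternatively, if a confirmatory whole-brain claim is wanted, split alpha between the regional family and the whole-brain search so that the total is 0.05, and recompute both sets of thresholds. In either case, print the corrected level and cluster extent for the whole-brain search.

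The section is written in the past tense and reports thresholds already obtained. If the analysis has been run, apply the same ranking and recomputed thresholds in reporting and interpretation. An alpha split chosen after the results are known could not be presented as prespecified, so ranking the regions first is then the more defensible option.

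The cost is a re-run of the threshold simulation, somewhat larger regional extents with some loss of sensitivity, and loss of confirmatory status for whole-brain clusters outside the a priori regions. No new data are needed.

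### Does the cluster threshold k = 13 cover a wider cingulate region than the one chosen in advance?

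*Combined protocol and SAP*

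**What the plan says.** The primary outcome section defines the outcome: "The principle outcome measure was a regressor for modulation of neural activity (BOLD responsivity) by intensity of fearful expression". Under MRI data group analysis there are two routes by which a cluster can be called significant on it. One is a whole-brain correction, with the cluster simulation run "using the autocorrelation function (-acf) with 10,000 Monte Carlo simulations for the whole-brain analysis"; the whole-brain cluster size is not stated. The other is a small-volume correction in named regions. For that route the plan states that "bilateral amygdala, anterior insula and midcingulate cortex, were selected a priori for ROI analysis". The sentence opens by pointing back to an earlier account of the regions, which is not in the supplied text. The cluster sizes come in the sentence after it, where the corrections "yielded thresholds of k = 13 for anterior/mid-cingulate cortex, k = 8 for anterior insula, and k = 2 for amygdala". All three rest on a voxel-level p of 0.005 and a corrected level of 0.05. The masks are anatomical and taken from the TTN27 atlas. Neither the atlas labels that make up each mask nor the voxel counts are given.

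**The concern.** Two adjacent sentences name the third region differently. The list has midcingulate cortex; the threshold sentence has anterior/mid-cingulate cortex, which on its face adds territory. The mask boundary matters because it decides which correction a cluster faces. Suppose the mask behind k = 13 takes in anterior cingulate tissue and only midcingulate cortex had been chosen in advance. A cluster of 13 or more voxels entirely in anterior cingulate would then be presented as a corrected, pre-specified finding on the main outcome, when it should have met the whole-brain threshold. The listed midcingulate region would meanwhile be tested with a cluster size that might be larger than it needs, at some cost in power.

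**Working it through.** **The names side by side.**

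| A priori list | Threshold sentence | k |
|---|---|---|
| bilateral amygdala | amygdala | 2 |
| anterior insula | anterior insula | 8 |
| midcingulate cortex | anterior/mid-cingulate cortex | 13 |

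There are three regions and three thresholds, with no separate fourth entry for anterior cingulate. The cingulate name is not the only one to change, since the word bilateral is dropped for the amygdala. That is what one would expect if the second sentence uses shorthand.

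**Can k = 13 be reproduced?** No. The stated inputs are the voxel-level threshold ("The initial threshold was set at p = 0.005"), a corrected level of 0.05, and the simulation method. Mask voxel count, voxel size, autocorrelation parameters, sidedness and the rule for joining voxels are all absent from the supplied text.

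**Can k = 13 show which region was used?** An illustration suggests not. Gaussian noise was simulated in box-shaped masks: 3,000 runs, two-sided voxel p = 0.005, positive and negative clusters formed separately, voxels joined by faces. The smallest k with error below 0.05 was:

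| Mask (voxels, assumed) | FWHM 2 voxels | FWHM 2.5 voxels | FWHM 3 voxels |
|---|---|---|---|
| 512 | 7 | 9 | 11 |
| 1,024 | 8 | 12 | 15 |
| 1,536 | 9 | 14 | 19 |

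Shapes, sizes and smoothness are all assumptions, so these are not estimates for this trial. They show that k rises with mask size. They also show that a value near 13 fits quite different mask sizes, depending on smoothness.

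**What if the mask is wider?** Let A be the mask on which k = 13 was computed, M the midcingulate part and R the remainder. Any cluster found within M or within R lies inside a cluster of A. The largest cluster in either part therefore cannot exceed the largest in A, and under the null

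P(largest cluster in M ≥ 13) ≤ P(largest cluster in A ≥ 13) < 0.05,

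and likewise for R. Three results follow without any assumed figure:

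1. The k required for midcingulate cortex alone is at most 13, so the stated value is adequate or strict for the listed region.
2. The chance of a false cluster in the remainder is already counted in the 5% for A and is not added to it.
3. The only possible effects are on how an anterior cingulate cluster is described and on some power in midcingulate cortex. Neither can be sized from the document.

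**The case for a change.** The strongest argument for acting is that this is a conflict between two sentences and not merely an omission, and that it touches the main outcome. The benign grammatical reading, in which the adjective anterior governs both insula and midcingulate cortex, does not fully remove it: anterior midcingulate is part of midcingulate cortex, so the slashed name would still be the broader one. Only the sponsor can say whether the names denote one mask, and asking costs little.

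Much of this stands. The wording does differ, the supplied text does not settle the matter, and keeping the pre-specified region fixed independently of where clusters appear is sound practice. It falls short because the harm needs two things that have not been shown: that the mask for k = 13 extends beyond the region chosen in advance, and that the earlier account to which the list refers leaves out anterior cingulate. That account is not available here, so its silence cannot be assumed. The slashed term may equally be a looser name for the same region.

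**Conclusion.** No change to the plan follows. What is established is an inconsistent label for one of three regions, together with a mask described by atlas only. No stated number or rule has been shown to be wrong. Followed as written, k = 13 keeps corrected error below 5% in the mask it was computed for and is never too lenient for midcingulate cortex. This rests on the threshold having been simulated on the mask that was actually applied, as the plan describes. The effect of a wider mask, if there was one, cannot be calculated from the document.

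Using one name and recording the atlas labels and voxel count is a clerical matter that analysts holding the mask file can deal with when they report. The conclusion would differ only if documentation predating the data named midcingulate cortex alone and the mask was found to be wider. In that case k would need recomputing on the narrower mask, and anterior cingulate clusters would have to meet the whole-brain threshold. Nothing supplied shows that this is so.
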